13.1.6 Reporting to Regulatory Authorities

SAEs and non-serious AEs will be reported to the appropriate regulatory authorities by RB, in accordance with the authorities' requirements.

13.1.7 Follow-up of Patients Experiencing Adverse Events upon Completion of the Study or Withdrawal from the Study

All SAEs, and all AEs that cause premature withdrawal of the patient from the study, that have not resolved by the end of the study will be followed up by the Investigator until resolution or until the Investigator believes there will be no further change. This may involve the patient making additional visits to the site.

All other AEs will be followed up where possible to resolution or until the Investigator believes there will be no further change, whichever is the earlier.

The minimum data required are the final outcome and date, which may be obtained by the Investigator in a documented telephone conversation with the patient or patient's medical practitioner.

13.1.8 Procedures for Patients Experiencing Onset of Adverse Events after End of the Study

As the active study drug in this study is not absorbed, a serious adverse event that occurs within a day of the final dose of study medication should be reported and followed to resolution or until the Investigator believes there will be no further change (refer to Adverse Event Reporting section 13.1.4 for further details).

13.2 Overdose

In the event of an overdose of the trial medication, symptomatic treatment should be given. The patient may notice abdominal distension.

Overdoses are reportable to RB irrespective of the presence of an associated AE/SAE. The overdose and any associated AE/SAE will be captured on an AE CRF page/SAE form.

13.3 Pregnancy

If a patient is found to be pregnant after being dosed with IMP:

- Promptly notify RB (i.e. Clinical Project Manager) or CRO monitor (if CRO is Investigator's first port of call for reporting SAEs).
- Withdraw the patient from the study.
- Perform study completion assessments.
- Collect details of due date, etc.

Pregnancy follow-up will be conducted by RB GVG personnel as part of their drug safety monitoring responsibilities and will not form part of the study dataset.

Pregnancy should be reported to RB as an AE.

13.4 Clinical Laboratory Investigations

All blood samples will be collected and prepared according to the standard procedures of the hospital laboratory conducting the analyses at each of the study sites. Laboratory safety parameters will be analysed using standard validated methods.

The following investigations will be made:

Haematology

- Haemoglobin
- Red blood cells
- Mean cell haemoglobin concentration
- White blood cells
- Platelet count

Biochemistry

- Electrolytes: sodium, potassium, calcium
- Urea
- Creatinine
- Uric acid
- Glucose

- Inorganic phosphorous
- Alanine transaminase
- Aspartate transaminase

Pregnancy testing

- Women of child-bearing potential will undergo urine pregnancy testing (positive or negative).

The total volume of blood expected to be sampled for clinical laboratory safety investigations from an individual patient in the course of the study is not expected to exceed 30 ml.

13.4.1 Collection of Laboratory Samples

Blood samples will be collected and labelled in tubes provided by the local laboratory.

Urine samples will be collected mid-stream.

13.4.2 Labelling of Laboratory Samples

The site's standard labels will be used.

13.4.3 Reference Ranges

Up-to-date reference ranges for the above investigations must be obtained for each site performing analyses prior to the start of the study and be updated as appropriate during the course of the study.

13.4.4 Laboratory Results Review

The Investigator will review the results and comment, on the laboratory results sheet, upon all abnormal values, identifying those that are clinically significantly abnormal. The Investigator will sign and date the laboratory results sheet, to indicate that the review has taken place.

A copy of these results will be provided to the [REDACTED] monitor.

13.4.5 Good Clinical Laboratory Practice (GCLP) Compliance

Confirmation of compliance with GCLP will be required from the laboratories involved prior to the start of the study.

The laboratories will be requested to provide documented evidence of GCLP compliance. This may be a statement of compliance issued by the appropriate national authority, or details of accreditation by a recognised organisation.

An independent inspection of the laboratories by [REDACTED] or RB may be conducted.

13.5 Vital Signs, Physical Findings and other Observations Related to Safety

Vital signs and physical examinations will be conducted at screening and final or early termination visits. A 12-lead ECG and endoscopy will be conducted and the results will be reviewed by the investigator at screening as part of the screening procedures. Patients will be asked about adverse events at follow-up visits.

14 STATISTICAL CONSIDERATIONS

The statistical analysis will be undertaken in collaboration with Quintiles.

A detailed Statistical Analysis Plan will be finalised before the code for all patients is broken and prior to analysis of the study being carried out.

Any deviations from the analyses described below will be included in the Statistical Analysis Plan, which will form Appendix 16.1.9 of the clinical study report.

14.1 Sample Size Justification

In a previous pilot study conducted in the UK (GA1203), a least square mean difference (Gaviscon – Placebo) of -0.61 was obtained from the ANCOVA model comparing the change in the GERD dimension score from the RDQ after 1 week. The root mean squared error (RMSE) from the ANCOVA model, which included treatment as a fixed effect and the day 0 RDQ GERD dimension score as a covariate, was 0.9735.

In the same study, a least square mean difference (Gaviscon – Placebo) of -0.43 was obtained from the ANCOVA model comparing the change in the Dyspepsia dimension score from the RDQ after 1 week. The root mean squared error (RMSE) from the ANCOVA model, which included treatment as a fixed effect and the day 0 RDQ Dyspepsia dimension score as a covariate, was 1.121.

For the purposes of sample size estimation using the module for a two-group t-test between equal means in NQuery Advisor 7.0, the least square means difference and RMSE from GA1203 will be used to estimate the effect sizes. The effect sizes using these results would be estimated as 0.627 for the GERD dimension and 0.384 for the Dyspepsia dimension.

In other previous studies, different endpoints to the RDQ were used to demonstrate the efficacy of Gaviscon Original Liquid compared to Placebo Liquid. The percentage of patients that rated a positive improvement in symptoms were reported. In a study conducted in the UK (0900901), 74% of Gaviscon Original patients had a positive improvement of symptoms compared to only 44% of Placebo patients. When a similar study was conducted in China (GA0917), the corresponding results were 77% for Gaviscon Original and 67% for Placebo, thus suggesting an increased Placebo effect in the Chinese population compared to the UK population.

Assuming a reduced effect size of 0.2 for the Dyspepsia dimension, this would require a total of 1054 patients with evaluable dyspepsia data from the RDQ to have 90% power to show a statistical significant difference at the 5% level using a two-group t-test. The actual analysis method to be used would be an ANCOVA model with treatment as a fixed effect, centre as a random effect and the day 0 RDQ Dyspepsia dimension score as a covariate.

If an effect size of 0.4 is assumed for the GERD dimension, a sample size of 1054 patients would give more than 99% power to show a statistical significant difference at the 5% level using a two-group t-test. The actual analysis method to be used would be an ANCOVA model with treatment as a fixed effect, centre as a random effect and the day 0 RDQ GERD dimension score as a covariate.

To allow for 5% drop outs, 1100 patients will be randomised to ensure that 1054 patients have evaluable data for the Dyspepsia dimension score.

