9.4 Number of Patients

The sample size calculation, based on the UK pilot study date [10] and a previous pivotal China study, shows that 1054 evaluable patients need to complete the study (with the aim of having approximately 527 patients in each treatment group). An evaluable patient is defined as a randomised patient who completes the study treatment period and attends the end of treatment visit. In order to achieve this, it is estimated that approximately 1222 patients will have to be screened and approximately 1100 patients will have to be randomised.

Patients will receive a screening number on signing the informed consent. Patients will receive a separate randomisation number on being randomised to the study.

It is anticipated that between 25 and 50 sites will take part in the study. Each site will be asked to recruit between 10 and 200 patients.

Further details are provided in Section 14.1.

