14.4.3 Statistical Methods for Efficacy Analyses

All statistical tests performed will be 2-tailed with significance assessed at the 5% significance level. The null hypothesis at all times will be the equality of the treatments being compared.

Normality assumptions will be evaluated by an examination of the residual plots. Depending on the degree of departure from these assumptions, an alternate nonparametric approach may be used for supportive purposes.

The primary endpoint (change in RDQ GERD dimension score) will be analysed using an analysis of covariance (ANCOVA) model with a fixed effect term for treatment, centre as a random effect and the day 0 RDQ GERD dimension score as a covariate. Treatment group differences will be estimated using the least square means and presented with 95% confidence intervals and p-values to make inferences.

The change in symptom score for each dimension separately will be analysed identically to the primary endpoint although the included covariate will be the relevant dimension day 0 score rather than the GERD dimension score.

To preserve the type 1 error rate of 5% for the key secondary endpoint (change from day 0 in RDQ scores for dyspepsia dimension), a closed testing procedure will be applied. A significant comparison at the 5% level ($p<0.05$) for this key secondary endpoint will only be deemed as confirmatory evidence if the primary endpoint is also significant at the 5% significance level ($p<0.05$). All other secondary endpoints and/or any further sensitivity or alternate analyses for the primary and key secondary endpoint will serve as supportive evidence only and therefore no further adjustment for multiple comparisons will be made.

For the primary and key secondary endpoint, two additional separate exploratory ANOVA models will be conducted identical to those stated above but with one additional interaction term for the treatment by centre interaction (random effect) and treatment by baseline covariate interaction respectively.

The change scores in frequency and intensity for each dimension as well as the two OTE responses will be compared between treatments using a Wilcoxon Rank Sum Test stratified by centre.

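### Randomising 1100 patients with 5% drop-out leaves 1045 evaluable, not 1054; the stated allowance should read about 4%, and the effect on power is negligible

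*Protocol*

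**What the plan says.** The trial is sized on the key secondary endpoint, change in the RDQ dyspepsia score. Protocol 14.1 (repeated in 3.11) begins: "Assuming a reduced effect size of 0.2 for the Dyspepsia dimension". The number required is then given as "1054 patients with evaluable dyspepsia data from the RDQ to have 90% power", with sizing by a t-test that compares two groups at a significance level of 5%. Protocol 9.4 gives the split, "with the aim of having approximately 527 patients in each treatment group". Section 14.1 closes with the allowance for losses: "To allow for 5% drop outs, 1100 patients will be randomised to ensure that 1054 patients have evaluable data" on the dyspepsia dimension.

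The number randomised also appears in Protocol 3.6 and 9.4 and in SAP 4.1, as an approximate figure and without a drop-out rate. Section 9.4, for example, says "approximately 1222 patients will have to be screened and approximately 1100 patients will have to be randomised". These three places define an evaluable patient as one who was randomised, completed the treatment period and attended the end-of-treatment visit. Protocol 11.7.2 says that patients who withdraw are not replaced.

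**The concern.** The closing sentence of 14.1 makes a promise that fails under its own assumption. If 5% of 1100 patients are lost, fewer than 1054 remain. The target also has no slack: 527 per arm is the smallest group size that reaches 90% power at effect size 0.2, so nothing in it absorbs a shortfall. Dyspepsia is both the endpoint that sets the trial size and the only secondary endpoint that can be claimed as confirmatory. What is at stake is whether the sizing statement of a study meant for regulatory applications survives a one-line check, and whether the stated power does.

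**Working it through.** **Inputs**
- Two-sided 5% level. Protocol 14.4.3: "All statistical tests performed will be 2-tailed with significance assessed at the 5% significance level".
- Standardised effect sizes: 0.2 for dyspepsia and 0.4 for the GERD dimension (14.1).
- Two-group t-test (14.1), equal arms (9.4).
- Target 1054 evaluable, 1100 randomised, 5% drop-out (14.1).

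**Step 1: reproduce the evaluable number.** With N patients in total and n = N/2 per arm, the t statistic has N − 2 degrees of freedom and noncentrality d × √(n/2). At d = 0.2 and n = 527 the noncentrality is 0.2 × √263.5 = 3.247, and power from the noncentral t distribution is 90.04%. At n = 526 it is 89.98%. So 527 per arm, 1054 in total, is the minimum, and the plan's figure is reproduced exactly.

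**Step 2: apply the drop-out rate.**
- Patients left from 1100 after a 5% loss: 1100 × 0.95 = 1045.
- Shortfall: 1054 − 1045 = 9, or 0.9% of 1054.
- Number to randomise so that 1054 remain: 1054/0.95 = 1109.5, so 1110.
- The cruder inflation, 1054 × 1.05, gives 1107, so it does not produce 1100 either.
- Largest loss at which 1100 still leaves 1054: (1100 − 1054)/1100 = 46/1100 = 4.18%.

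**Step 3: effect on power.**

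| Evaluable patients | Dyspepsia, d = 0.2 | GERD dimension, d = 0.4 |
|---|---|---|
| 1054 | 90.04% | above 99.99% |
| 1045 | 89.79% | above 99.99% |

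The loss on dyspepsia is 90.04 − 89.79 = 0.25 percentage points. For scale, going from 1054 to 1045 patients has the same effect as assuming an effect size of 0.2 × √(1045/1054) = 0.199 instead of 0.200.

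**Step 4: how many drop-outs would have to supply data.** A 5% loss from 1100 is 55 patients. If 9 of them still contribute a dyspepsia score, the number analysed is 1045 + 9 = 1054.

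**The case against.** The strongest reply is that a drop-out is not the same as a missing dyspepsia score.

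- Protocol 11.3.2.3 and 11.7.1 have withdrawn patients complete the RDQ at an early-termination visit, and SAP 7.3 maps that visit to Visit 3 for by-visit summaries.
- Protocol 14.4 and SAP 15.2.2 impute no change for patients who do not return because of confirmed poor efficacy. The SAP limits this to patients with no early-termination visit.
- The ITT population (Protocol 14.2, SAP 6.3) keeps anyone with an at least partly completed on-treatment RDQ, as well as withdrawals for poor efficacy.

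Only 9 of 55 drop-outs need to be retained in this way. A reader might infer that 5%, 1100 and 1054 can never all be true. That goes too far, because they conflict outright only if a drop-out yields no data.

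This reply stands for the number analysed, but it does not rescue the sentence. Under the evaluable-patient definition in 3.6, 9.4 and SAP 4.1, a patient who stops early does not count, and the sizing text takes no credit for retained data. Withdrawals for other reasons who do not complete the Visit 3 assessments are treated as missing (Protocol 14.4).

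A second reply is that 1100 is only approximate. That is so in 3.6, 9.4 and SAP 4.1, and 1100 is within 0.9% of 1110. But the allowance sentence in 3.11 and 14.1 carries no such qualifier and promises a result.

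**Conclusion.** The arithmetic slip is real and minor. At the stated 5% loss, 1100 randomised leaves 1045 evaluable patients, and 1054 is reached only if loss is at most about 4.2%.

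A reader might go on to infer that the trial is underpowered, or that the stated 90% is not delivered. The documents do not support that. The plan states power as a whole number, and 89.8% rounds to it. The assumed effect size of 0.2 is itself a judgement, reduced from the pilot estimate of 0.384, and its uncertainty is far larger than a shift from 0.200 to 0.199. The primary endpoint keeps more than 99% power at either number.

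The power figures assume equal arms, the two-group t-test used for sizing and a true effect size of 0.2. Treating 1045 as a lower bound for the number analysed assumes that all losses, including completers whose dyspepsia score cannot be derived, stay within 5%.

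**What to change.** In Protocol 3.11 and 14.1, change the allowance sentence in one of two ways:

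1. keep 1100 and 1054, and give the allowance as about 4% (46 of 1100); or
2. keep 1100 and 5%, and say that about 1045 evaluable patients are then expected, with power of about 89.8% for dyspepsia at effect size 0.2.

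Either way, drop the word *ensure*. Sections 3.6 and 9.4 and SAP 4.1 need no correction, because they state no drop-out rate and their 1054 and approximate 1100 are compatible.

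The cost is one sentence in two places. Under the second option the stated power looks slightly less favourable. Enrolment, endpoints, analysis sets and analyses do not change.

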14.2 Data to be Analysed

The following defined populations will be used for the analysis of the study data.

All patient population: includes all patients recruited into the study. Data presentation will comprise information on patient disposition, withdrawals and protocol deviations as well as baseline data.

Safety population: includes those recruited into the study and receive at least one dose of the study medication. Summaries and analyses for all safety endpoints will be conducted on this population.

Intent to treat (ITT) population: includes those recruited into the study and have at least partially completed RDQ questionnaire for the trial therapy period or are known to have withdrawn from the study due to poor efficacy. Summaries and analyses for all primary and secondary endpoints will be conducted on this population.

Per protocol (PP) population: includes all patients from the ITT population who have adequate compliance with the treatment during the study (defined as $\geq 75\%$ study medication used from return tablet count) and no major protocol deviations. This PP population will be defined based upon a review of blinded data prior to database lock. All summaries and analyses for all primary and secondary endpoints will be additionally conducted using this population to support the corresponding ITT results.

If there is a discrepancy in patient numbers between the all patient population and any other population, then baseline data will be summarised additionally for that population and for those patients that are excluded from that population.

14.3 Patient Disposition and Characteristics

Descriptive summary statistics will be provided for demographic characteristics for each treatment group and all patients. For continuous parameters, mean, standard deviation, median, minimum, and maximum will be provided. For categorical parameters, the cell frequencies and percentage of patients in each demographic category will be provided.

14.4 Efficacy Analyses

Efficacy data will be recorded from the RDQ questionnaire and the patient overall treatment evaluation (OTE).

All efficacy data will be listed in the appendices of the study report and summarised for the ITT and PP populations by treatment group (n as the number of observations, mean, median, SD, minimum and maximum). Categorical variables will be summarised by treatment group using frequency distributions (showing cell frequencies and percentages).

For those patients that do not return for Visit 3 because of confirmed poor efficacy from the treatment between Day 1 and Day 6, all efficacy data at Visit 3 will be imputed as no change from the day 0 values (BOCF). All other withdrawn patients that do not have the reason of withdrawal confirmed as poor efficacy and do not complete the Visit 3 assessments will be treated as missing. If the number of such patients is high, a sensitivity analysis will be conducted to assess the robustness of this imputation and the effect on results.

14.4.1 Primary Efficacy Analysis Endpoint

The primary study endpoints are to compare the change from day 0 in RDQ symptom scores for the GERD dimension (heartburn and regurgitation) after a 7-day treatment period of a regimen of two Compound Sodium Alginate Double Action Chewable Tablets taken four times daily compared with a matched placebo.

14.4.2 Secondary Efficacy Endpoints

The key secondary endpoint will compare between the two cohorts (Compound Sodium Alginate Double Action Chewable Tablets and placebo) for a 7-days treatment period for the following parameter:

- Change from day 0 in RDQ scores for dyspepsia dimension

Other secondary endpoints will compare between the two cohorts (Compound Sodium Alginate Double Action Chewable Tablets and placebo) for a 7-days treatment period for the following parameters:

- OTE as a measure for patient's responsiveness/satisfaction

- Change from day 0 in RDQ scores for heartburn dimension.
- Change from day 0 in RDQ scores for regurgitation dimension.

14.4.3 Statistical Methods for Efficacy Analyses

All statistical tests performed will be 2-tailed with significance assessed at the 5% significance level. The null hypothesis at all times will be the equality of the treatments being compared.

Normality assumptions will be evaluated by an examination of the residual plots. Depending on the degree of departure from these assumptions, an alternate nonparametric approach may be used for supportive purposes.

The primary endpoint (change in RDQ GERD dimension score) will be analysed using an analysis of covariance (ANCOVA) model with a fixed effect term for treatment, centre as a random effect and the day 0 RDQ GERD dimension score as a covariate. Treatment group differences will be estimated using the least square means and presented with 95% confidence intervals and p-values to make inferences.

The change in symptom score for each dimension separately will be analysed identically to the primary endpoint although the included covariate will be the relevant dimension day 0 score rather than the GERD dimension score.

To preserve the type 1 error rate of 5% for the key secondary endpoint (change from day 0 in RDQ scores for dyspepsia dimension), a closed testing procedure will be applied. A significant comparison at the 5% level ($p<0.05$) for this key secondary endpoint will only be deemed as confirmatory evidence if the primary endpoint is also significant at the 5% significance level ($p<0.05$). All other secondary endpoints and/or any further sensitivity or alternate analyses for the primary and key secondary endpoint will serve as supportive evidence only and therefore no further adjustment for multiple comparisons will be made.

For the primary and key secondary endpoint, two additional separate exploratory ANOVA models will be conducted identical to those stated above but with one additional interaction term for the treatment by centre interaction (random effect) and treatment by baseline covariate interaction respectively.

The change scores in frequency and intensity for each dimension as well as the two OTE responses will be compared between treatments using a Wilcoxon Rank Sum Test stratified by centre.

